8.4. Data Sources

All data collected in this study are intended to capture the real-world treatment patterns and outcomes for patients with HR+/HER2- metastatic/locally advanced BC. An electronic case report form (eCRF) will be used for data collection. The eCRF must be signed by the investigator. The signature serves to attest that the information contained in the eCRF is true. At all times, the investigator has the final responsibility for the accuracy and authenticity of all clinical and laboratory data entered into the eCRFs.

Data for this study will be obtained via the sources outlined below.

8.4.1. Patient Medical Charts

The investigator or authorized medical staff will record clinical and treatment data from patients' existing medical records into an eCRF following each patient's standard of care clinic visit.

8.4.2. Patient Questionnaires and Quality of Life

All patients enrolled in the study will be asked to participate in completing the Quality of Life Questionnaire, EORTC QLQ-C30, to be collected at baseline (before starting palbociclib) then every 3 months \pm 2 weeks after initiating treatment with palbociclib, for the first year of treatment, in accordance with routine standard of care visits. After the first year of treatment with palbociclib, EORTC QLQ-C30 will be collected every 6 months \pm 4 weeks until the end of treatment with palbociclib, in accordance with routine standard of care visits.

Patients will complete these questionnaires on a paper form.

8.5. Study Size

This is an observational study of drug usage without any pre-defined hypothesis to be tested; rather, it addresses descriptive objectives. Sample size calculations were performed per country taking into account population size, estimated MBC prevalence, and a margin of error of 5%. A minimum sample size of 15 patients per country (total sample size of 105 patients) was estimated on this basis.

A planned total sample size of approximately 350-410 patients ([Table 3](#)) will be applied to ensure adequate exploration of the objectives and sufficient generalizability.

Table 3. Planned Number of Subjects and Centers per Country

Country	Estimated Number of Centers	Estimated Number of Subjects
Egypt	5	60
Gulf (UAE/Qatar)	2	20
Jordan	1	20
Lebanon	6	65
Morocco	2	15
KSA	3	20
Total	19	200

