In the United States (US) patient subgroup, the 12-month progression free rate was 84.1% for patients treated with palbociclib plus aromatase inhibitor and 79.8% for those treated with palbociclib plus fulvestrant; 12-month survival rates were 95.1% for palbociclib plus aromatase inhibitor and 87.9% for palbociclib plus fulvestrant.³⁰ In another retrospective chart review study conducted in the US, real-world effectiveness was evaluated among patients using palbociclib plus letrozole as first-line treatment; the 6-month, 12-month and 18-month PFS rates were 92.7%, 75.5%, and 51.6%, respectively, while the 6-month, 12-month, and 18-month overall survival rates were 97.5%, 95.3% and 92.5%, respectively.³¹

In a prospective real-world study, “Palbociclib in Hormone Receptor–Positive Advanced Breast Cancer: A Prospective Multicenter Noninterventional Study (POLARIS)”, measures of functional status were assessed in adults aged ≥ 70 years who were using palbociclib combination therapy.³² The results showed that measures of functional status (as assessed via the Activities of Daily Living [ADL] screening tool, Geriatric 8 [G8] screening tool, and Eastern Cooperative Oncology Group [ECOG] performance status) were generally maintained during the first 6 months of therapy, indicating that functional status was essentially preserved in elderly population receiving palbociclib combination therapy.³²

In the AfME region, palbociclib was first approved in UAE in early 2015 in combination with letrozole for the treatment of post-menopausal women with ER+/HER2- MBC as initial endocrine-based therapy for their disease. Since then, approval in Lebanon and KSA followed, and now palbociclib is available in most AfME countries.

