7.1. Primary Objectives

- To determine clinical outcomes including (but not limited to):
 - Proportion of patients who are progression free and alive at specific intervals (eg, 12, 18 months).
 - Proportion of patients alive 1- and 2-years post palbociclib combination initiation - depending on availability of follow-up data.

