8. RESEARCH METHODS

8.1. Study Design

This is a prospective, non-interventional (NI), multicenter study being conducted in Africa Middle East (AfME) countries. The aim is to understand palbociclib treatment patterns, clinical outcomes and QoL for patients with metastatic/locally advanced BC being treated in routine clinical practice in 7 AfME countries: Egypt, Jordan, KSA, Lebanon, Morocco, Qatar and UAE.

Approximately 200 patients from 19 centers across the 7 countries will be enrolled. The recruitment period (ie, from first patient into last patient in) will span over 18 months.

[figure not shown]
Patients will be enrolled at the time of treatment initiation with palbociclib and will be followed up over a 24-month period at time intervals per routine care, or until patient's withdrawal from the study or death (whichever comes first). Prospective data on clinical characteristics, treatment patterns, clinical outcomes and QoL will be collected ([Figure 1](#)).

Participation in this study is not intended to change the routine treatment patients receive, as determined by their prescribing physicians; all treatment decisions, type and timing of the disease monitoring are per routine clinical care, and at the discretion of treating physician and patient.

All assessments described in this protocol are performed as part of normal clinical practice or standard practice guidelines for the patient population and healthcare provider specialty in the countries where this non-interventional study is being conducted.

All assessments described in this protocol are performed as part of normal clinical practice or standard practice guidelines for the patient population and healthcare provider specialty in the countries where this non-interventional study is being conducted.

Figure 1. Study Design

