2.2.1. Primary Objectives

To determine clinical outcomes including (but not limited to):

- Proportion of patients who are progression free and alive at specific intervals (6, 12, 18 and 24 months). Patients who are not censored (see [Section 3.1](#)) at a certain time point will be included in the analysis.
- Proportion of patients alive after 1 and 2 years post palbociclib combination initiation.

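### Protocol 8.5 bases its minimum size on disease prevalence and a 5% margin and states no precision for the primary outcomes; 200 patients give about ±5–7 points on 12- and 18-month progression-free status

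*Protocol*

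**What the plan says.** Protocol 8.5 (Study Size) says that no hypothesis is tested and that the objectives are descriptive. It then says: "Sample size calculations were performed per country taking into account population size, estimated MBC prevalence, and a margin of error of 5" per cent, and continues: "A minimum sample size of 15 patients per country (total sample size of 105 patients) was estimated on this basis". It gives no prevalence, population size, confidence level or formula, and does not name the quantity to which the margin applies.

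The next paragraph gives "A planned total sample size of approximately 350-410 patients", justified only by exploration of the objectives and generalizability. Table 3 in the same section adds to 200, and Protocol 8.1 agrees: "Approximately 200 patients from 19 centers across the 7 countries will be enrolled".

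The primary outcomes in Protocol 7.1 are "Proportion of patients who are progression free and alive at specific intervals (eg, 12, 18 months") and "Proportion of patients alive 1- and 2-years post palbociclib combination initiation". SAP 2.2.1 lists the first as "Proportion of patients who are progression free and alive at specific intervals (6, 12, 18 and 24 months"). Neither document gives an expected value or a target precision for any of these.

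**The concern.** In a study without tests, the width of the intervals is the only statistical argument for the sample size. The one argument offered concerns how common the disease is in a population. Everyone enrolled has metastatic or locally advanced disease under the inclusion criteria (Protocol 8.2.1), so the data cannot estimate that quantity, and a margin around it says nothing about outcomes among treated patients.

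Two things are at stake. First, 5% is the only precision figure in the plan, and it does not describe the primary results. Second, Amendment 2 reduced the study to 200 patients without saying what that does to precision, while the text of 8.5 still carries the larger total.

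**Working it through.** **Inputs.** The margin (5 points), the minimum (15 per country, 7 countries) and the country rows come from Protocol 8.5. The total of 200 comes from Table 3 and Protocol 8.1. The outcome rates are those cited in Protocol 6.1:
- US subgroup of the IRIS study: "the 12-month progression free rate was 84.1% for patients treated with palbociclib plus aromatase inhibitor and 79.8% for those treated with palbociclib plus fulvestrant". Survival at 12 months was 95.1% and 87.9% respectively.
- US first-line chart review: progression-free 75.5% at 12 months and 51.6% at 18 months; 12-month survival 95.3%.
- Argentina subgroup of IRIS: 12-month survival 93%.

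The 95% level is an assumption for 8.5. The SAP uses it for its Kaplan-Meier intervals.

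**Step 1: the plan's own figure.** 15 × 7 = 105, as stated. The 15 cannot be reproduced, because its inputs are missing. Working backwards from n = 1.96² p(1−p)/d² with n = 15 and d = 0.05:

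p(1−p) = 15 × 0.0025 / 3.8415 = 0.00976, so p ≈ 0.0099, about 1%.

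At 90% confidence p would be about 1.4%, and at 99% about 0.57%. A finite-population correction with populations from 100,000 to 100 million leaves n at 15. A value near 1% could be a prevalence. It is not close to any progression-free or survival rate listed above.

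**Step 2: precision for the primary outcomes.** Half-width in points = 100 × 1.96 × √(p(1−p)/n), with complete follow-up:

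| Cited rate | n = 15 | n = 20 | n = 60 | n = 65 | n = 200 |
|---|---|---|---|---|---|
| 12-month progression-free, 84.1% | 18.51 | 16.03 | 9.25 | 8.89 | 5.07 |
| 12-month progression-free, 79.8% | 20.32 | 17.60 | 10.16 | 9.76 | 5.56 |
| 12-month progression-free, 75.5% | 21.77 | 18.85 | 10.88 | 10.46 | 5.96 |
| 18-month progression-free, 51.6% | 25.29 | 21.90 | 12.65 | 12.15 | 6.93 |
| 12-month survival, 87.9% | 16.50 | 14.29 | 8.25 | 7.93 | 4.52 |
| 12-month survival, 93% | 12.91 | 11.18 | 6.46 | 6.20 | 3.54 |
| 12-month survival, 95.1% | 10.92 | 9.46 | 5.46 | 5.25 | 2.99 |
| 12-month survival, 95.3% | 10.71 | 9.28 | 5.36 | 5.15 | 2.93 |

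The simple (Wald) interval is poor at n = 15 with rates near 95%, where its upper limit exceeds 100%. Wilson half-widths at n = 15 run from about 13 to 23 points instead of 11 to 25.

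**Step 3: size needed for 5 points.** The same formula gives 206 patients at 84.1%, 248 at 79.8%, 285 at 75.5% and 384 at 51.6%. For 12-month survival it gives 69 to 164. At the 350 and 410 still in the text, 18-month progression-free status would have half-widths of 5.24 and 4.84 points, against 6.93 at 200.

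**Step 4: time points without a cited rate.** The documents give no 2-year survival rate. Assuming 80% to 90%, the half-width at 200 is 1.96 × √(0.16/200) = 5.5 down to 1.96 × √(0.09/200) = 4.2 points. They also give no 24-month progression-free rate; near 50% it would be about 6.9 points. At the SAP's 6-month time point, the cited rates of 92.7% to 95% give 3.6 to 3.0 points at 200.

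**Step 5: countries.** Table 3 has rows of 15 to 20 patients and two larger ones, Egypt (60) and Lebanon (65). For 12- and 18-month progression-free status these give about ±16–25 and ±9–13 points. UAE and Qatar share one row of 20, so at least one of them has 10 or fewer, below the stated minimum of 15.

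**The case against.** The strongest reply is that 8.5 says nothing false. It never attaches 5% to a progression-free or survival proportion, calls the objectives descriptive, and multiplies 15 by 7 correctly. That stands: this is a gap in the justification, not a broken promise. A reader might infer that the protocol guarantees outcome results to within 5 points, but the text does not say so.

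The prevalence reading and the 1% are also inferences, since the inputs are unstated. The defect does not depend on them: whatever the margin was attached to, the listed inputs do not include an outcome rate.

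The practical harm is limited. Country strata are exploratory and conditional on adequate numbers (Protocol 8.7, SAP 3.2). The progression-free rows in SAP Table Shells 2–9 carry 95% confidence intervals, so their width will be visible; the rows for patients alive carry none. The amendment log already records recruitment difficulty as the reason for 200. These points reduce the consequence, but they do not make a prevalence calculation a basis for the size.

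**Conclusion.** The concern holds as a failure of the size justification. The calculation in 8.5 does not bear on the primary outcomes, and no other precision statement does. At the cited rates, 200 patients give 5.1–6.0 points for 12-month and 6.9 points for 18-month progression-free status. The excess over 5 points is trivial at 84.1% (5.07, with 206 needed) and clear at 75.5% and 51.6%.

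A reader might go further and conclude that 200 is too few, or that it misses 5 points on every primary outcome. The documents support neither. They set no precision target for these outcomes, and 12-month survival at all cited rates is estimated to within 2.9–4.5 points. The 11–25 point range belongs to the stated minimum of 15, not to every country.

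The figures rest on 95% confidence, the cited rates applying in this region, and complete follow-up. Loss to follow-up would widen the Kaplan-Meier intervals. The survival proportion in SAP 6.1 is a crude ratio over all treated patients, so for that outcome missing follow-up is mainly a question of bias.

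**What to change.** Rewrite the two paragraphs of Protocol 8.5:
- Remove the prevalence and 5% calculation as the basis for the size.
- Replace 350–410 with 200, to agree with Table 3 and Protocol 8.1. SAP 2.1 carries the same old total and should follow.
- State that 200 is set by feasibility.
- Give the precision it delivers: about ±5–7 points for 12- and 18-month progression-free proportions, about ±3–4.5 points for 1-year survival and, for 2-year survival, a range under a stated assumption (for example ±4.2–5.5 points if it lies between 80% and 90%). Note that loss to follow-up reduces the precision of the Kaplan-Meier estimates.
- State that country results are descriptive only: for 12- and 18-month progression-free status about ±16–25 points in the rows of 15–20 patients and about ±9–13 points in Egypt and Lebanon. Say that UAE and Qatar share 20 patients, so at least one falls below 15.

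This is a wording change. It needs no extra patients and alters no analysis; the only downside is that the stated precision becomes less favourable.

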2.1. Study Design

This is a prospective, non-interventional (NI), multicentre study being conducted in Africa Middle East (AfME) countries. The aim is to understand palbociclib treatment patterns, clinical outcomes and QoL of patients with metastatic/locally advanced BC being treated in routine clinical practice in seven AfME countries: Egypt, Jordan, Lebanon, UAE, Qatar, Morocco and KSA.

Participation in this study is not intended to change the routine treatment patients receive, as determined by their prescribing physicians; all treatment decisions, type and timing of the disease monitoring are per routine clinical care, and at the discretion of the treating physician and patient.

Study population

[figure not shown]
Patients with HR+/HER2- metastatic/locally advanced BC within Egypt, Jordan, Lebanon, UAE, Qatar, Morocco and KSA will be enrolled from a geographically representative population as well as from diverse treatment settings (eg, academic and community sites). Patients whose treatment decision with palbociclib combination has been made by their treating physician and meet the eligibility criteria will be invited to participate in the study in a consecutive manner and over 12 months of recruitment.

Approximately 350-410 patients from 19 centers across the seven countries will be enrolled. The recruitment period (ie, from first patient in to last patient in) will span over 12 months.

Patients will be enrolled at the time of treatment initiation with palbociclib, and will be followed up over a maximum of 24-month period at time intervals per routine care, or until the end of Palbociclib treatment, progression or patients' withdrawal from the study (whichever comes first). Eligibility will be assessed at the date of the enrollment.

Prospective data on clinical characteristics, treatments patterns, clinical outcomes and QoL will be collected in accordance with routine standard of care visits (Figure 1). Data will be collected at enrollment (time of treatment initiation), during treatment with Palbociclib (at time intervals per routine care) and after treatment with palbociclib. After the end of treatment with palbociclib, data related to the first immediate subsequent treatment received will be collected.

Figure 1. Study Design

FPI: first patient in; LPI: last patient in; LPO: last patient out; QoL: quality of life

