3. ANALYSIS SETS/POPULATIONS

3.1. Full Analysis Set

The Full Analysis Set will contain all patients who fulfil the eligibility criteria. Date of enrollment is the date of Palbociclib treatment initiation (baseline).

Censoring rules: The maximum follow-up of a patient is 24 months. Patients will be censored at the end of Palbociclib treatment, or if the treatment continues, at 24 months. Other censoring events before 24 months are patient's withdrawal, disease progression or death, whichever occurs first. Patients' subsequent treatments after Palbociclib treatment discontinuation /disease progression will be recorded. Patients who are lost to follow-up will be censored at their last visit. For some clinical outcomes, different censoring rules will be applied as described in [Section 6.1](#), [Section 6.2](#), and [Section 6.3](#).

Data collection is estimated to start in Q2 2021 and it will end in Q4 2024.

Table and Figure Shells are presented in [ANNEX 2](#).

Patient inclusion and exclusion criteria are explained in [Section 2.1](#). Summary of patient enrolment per country and study site will be described as shown in [Table Shell 1](#).

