6.3. Analysis for the Exploratory Objectives

For the exploratory analyses, time to response (TTR), time to progression (TTP)/ progression free survival (PFS) will be studied and results will be presented as shown in [Table Shell 54](#). The stratified tables will be presented as in Table Shells [55-61](#).

TTR is defined as the length of time (in days) from the initiation of Palbociclib treatment until the first reported disease response (complete or partial).³⁴ Censoring rules presented in [Section 3.1](#) will be applied.

TTP is defined as the length of time (in days) from the initiation of Palbociclib treatment until the first reported disease progression.³⁴ Patients will be censored at the end of Palbociclib treatment, death, time of withdrawal, or end of the 24-month follow-up, whichever occurs first, at the respective time point. Specifically, death is not included in TTP but is considered as censoring event.

PFS is defined as the length of time (in days) from the initiation of Palbociclib treatment until the first reported disease progression or death due to any cause, whichever occurs first.³⁴ The disease progression will be considered at the first follow-up visit after the Palbociclib treatment initiation when the overall tumor response recorded is progressive disease. Patients with no disease progression documented will be censored at the last available medical record entry or end of the follow-up period. Patients who are lost to follow-up will be censored at their last visit.

Survival analyses will be used to estimate time to event endpoints TTR, TTP and PFS. The results of the survival analysis will be presented as the Kaplan-Meier survival curves and their 95% confidence intervals (CIs) that will be calculated using the log-log transformation of the survival probabilities.³⁶ Together with the Kaplan-Meier plots, the number of patients at risk at time intervals (eg, 90 days or as seen appropriate for the study) will be reported. [Figure Shells 1 and 2](#) show how time to response (TTR) and progression free survival (PFS) will be visualized as Kaplan-Meier plots including the number of patients at different time intervals. Kaplan-Meier plots can be presented by other categories (see [Section 3.2](#)), if enough data are available. Moreover, the results of the survival analysis will be reported as a descriptive summary table including the number of patients at risk, the number of patients

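### Protocol 8.5 gives a planned total (350-410) that its own Table 3 contradicts (200), and justifies its per-country minimum by prevalence precision instead of precision for the primary proportions

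*Protocol*

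**What the plan says.** Protocol Section 8.5 says the calculation was done country by country, "taking into account population size, estimated MBC prevalence" and a 5% margin of error. It concludes: "A minimum sample size of 15 patients per country (total sample size of 105 patients) was estimated on this basis". It gives no prevalence, population size, confidence level or formula, and it names no study outcome to which the margin applies.

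The next paragraph reads "A planned total sample size of approximately 350-410 patients" and refers to Table 3. Table 3 lists Egypt 60, Gulf (UAE/Qatar) 20, Jordan 20, Lebanon 65, Morocco 15 and KSA 20, with a total of 200. Section 8.1 agrees with the table: "Approximately 200 patients from 19 centers across the 7 countries will be enrolled". Section 4 records the cut to 200 and the extension of recruitment to 18 months as amendment 2, dated 8 November 2022.

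The primary objectives (Section 7.1) are proportions: progression free and alive at, for example, 12 and 18 months, and alive at 1 and 2 years.

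The SAP states that it was built on protocol version 2.0. Its Section 2.1 has "Approximately 350-410 patients from 19 centers across the seven countries will be enrolled" and 12 months of recruitment. Its Section 3.1 has "Data collection is estimated to start in Q2 2021 and it will end in Q4 2024". Section 3.2 and Table Shell 5 report seven separate countries, with UAE and Qatar in their own columns and a 95% interval for each progression-free percentage.

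**The concern.** A descriptive study has no power calculation, so expected precision is the only available justification for its size. Section 8.5 offers one, but for a quantity outside the objectives, and it says nothing about precision for the outcomes that will be reported. The leftover 350-410 adds to the problem: that range happens to give about ±5 points at 50%, so a reader of the text could conclude that the overall estimates are roughly that precise, when 200 patients give about ±7. The only number offered for countries is 15. A reader could take it as adequate for by-country results, where the intervals would in fact be very wide. For two of the seven countries, the allocation does not meet even that minimum.

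**Working it through.** **Inputs.** The margin (5%, read as ±5 percentage points) and n = 15 come from Protocol 8.5. The 95% level is an assumption: 8.5 states none, but the SAP reports 95% intervals. The planning rates come from Protocol 6.1, from the US chart review of first-line palbociclib plus letrozole: progression free 75.5% at 12 months and 51.6% at 18 months; alive 95.3% and 92.5% at the same times. No 2-year survival rate is cited.

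**Sums.** 7 × 15 = 105 reproduces. Table 3 patients: 60 + 20 + 20 + 65 + 15 + 20 = 200. Centers: 5 + 2 + 1 + 6 + 2 + 3 = 19. The table is internally correct; the 350-410 sentence that cites it is not.

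**Where 15 could come from.** The precision formula is n = 1.96² p(1−p)/0.05². Setting n = 15 gives p(1−p) = 15 × 0.0025/3.8416 = 0.00976, so p = 0.99%. At 90% confidence p would be 1.41%, and at 99% it would be 0.57%. At 95%, an assumed prevalence of 0.95% gives exactly 15 after rounding up; 0.5% gives 8, 2% gives 31 and 5% gives 73. So 15 is reachable for a prevalence near 1%, but it cannot be confirmed because the inputs are not stated. A margin of ±5 points around 1% would also say little.

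Population size does not rescue the figure for the outcomes. With a finite-population correction, 15 would suffice for proportions from 50% to 95.3% only if a country's whole target population were about 16 to 19 patients.

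**Precision for the primary proportions.** Half-width = 1.96 √(p(1−p)/n), in percentage points, with no censoring:

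| Rate | n = 15 | n = 20 | n = 65 | n = 200 | n for ±5 |
|---|---|---|---|---|---|
| 50% | 25.3 | 21.9 | 12.2 | 6.9 | 385 |
| 51.6% | 25.3 | 21.9 | 12.1 | 6.9 | 384 |
| 75.5% | 21.8 | 18.8 | 10.5 | 6.0 | 285 |
| 92.5% | 13.3 | 11.5 | 6.4 | 3.7 | 107 |
| 95.3% | 10.7 | 9.3 | 5.1 | 2.9 | 69 |

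At 50%, the 105 minimum gives ±9.6, and 350-410 gives ±5.2 to ±4.8. The exact interval at n = 15 never has a half-width below 10.9 points (15 of 15 gives 78.2% to 100%).

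**Gulf allocation.** Two countries at 15 each need 30; Table 3 plans 20 for both. If they split evenly, n = 10 gives 1.96 √(0.25/10) = ±31 points at 50%.

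**Dates.** Taking 15 July 2021 (Protocol Section 5) as first patient in, which is an assumption, 18 months of recruitment plus 24 of follow-up reaches 15 January 2025. That is before the protocol's end of data collection, 30 April 2025, but after the SAP's Q4 2024.

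**The case against.** The strongest reply is that 8.5 never promises ±5 points for progression-free or overall survival. That stands. A reader might infer that the protocol claims 5% precision for its outcomes and fails to deliver it, but the text ties the margin to MBC prevalence. Nor is 15 shown to be a miscalculation: it fits a plausible prevalence, and 105 is right. The fault is that the basis is irrelevant to the objectives and cannot be reproduced.

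It would also go too far to say that 15 patients cannot give ±5 points for any outcome whatever. Under the normal-approximation formula they can for proportions at or beyond about 1% or 99%. The statement is safe for the 12- and 18-month rates the protocol cites. Those rates come from a first-line US population, whereas this study also enrols second-line and fulvestrant patients, so they are planning values only.

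The country analyses are labelled exploratory and depend on adequate numbers, no testing is planned, and Table Shell 5 prints intervals, so the width will be visible. This reduces the risk of over-reading. It does not remove it, because no threshold for adequate numbers is given and 15 is the only figure available.

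The SAP's 350-410, 12 months and Q4 2024 might be read as further evidence against the sample-size basis. They are declared version lag: the SAP is dated February 2022, before the November 2022 amendment. They need updating and prove nothing more.

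Finally, the intended total can be recovered from Table 3, Section 8.1 and the amendment log, so this is a correction of documents and not a failure of the design.

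**Conclusion.** The point holds in this form. The 350-410 in Protocol 8.5 is wrong in current text, contradicted by the table it cites and by Section 8.1. The 15-per-country minimum rests on precision for a quantity the study does not estimate, from unstated inputs, and it does not support the primary proportions: half-widths are about 11 to 25 points at the cited 12- and 18-month rates. At 200 they are about 6.9 points at 51.6%, 6.0 at 75.5% and 3.7 at 92.5%, and the protocol gives no precision for that number. Table 3 cannot meet the minimum in both UAE and Qatar.

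These figures assume a 95% level, the cited rates as planning values, and no censoring. The progression-free proportions are Kaplan-Meier estimates, with censoring under SAP Sections 3.1 and 6.3, so the half-widths are best case. The conclusion is that the size is misstated and its justification is missing; the documents do not support a claim that 200 is too few for a descriptive study.

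**What to change.** In Protocol 8.5:

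- Restate the planned total as about 200.
- Replace the prevalence-based 5% margin and the 15-per-country basis with expected 95% half-widths for the primary proportions at n = 200 (about 6.9 points at 51.6%, 6.0 at 75.5%, 3.7 at 92.5%). Add the by-country range: about ±12 to ±25 points at 50% for 65 down to 15 patients, and wider for UAE or Qatar if reported separately.
- State the confidence level and the planning rates, and label the figures as best case before censoring.
- Reconcile the Gulf allocation with the minimum, either by dropping the minimum or by reporting UAE and Qatar pooled as in Table 3. Pooling is an option, not a requirement; separate reporting with intervals is defensible if no per-country minimum is claimed.

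In the SAP, rebase on protocol version 3.0: 200 patients and 18 months of recruitment in Section 2.1, and data collection from 15 July 2021 to 30 April 2025 in Section 3.1. Align the country shells with whatever is decided for the Gulf.

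The cost is wording in two documents. No patients are added and no analysis method changes; the overall and by-country precision a reader can expect becomes explicit and less favourable than the present text suggests.
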